### Statistical Analysis

Please refer to the Statistical Analysis Plan (SAP).

### **POSSIBLE BENEFITS**

We cannot guarantee any personal benefits from participating in this study. However, potential benefits to the subject may include shorter duration of receiving IV vasopressors, and shorter length of stay in the ICU and hospital. Earlier discharge from the ICU and hospital reduces the risk of developing nosocomial infections and reduces the total cost of the hospital admission. Information gathered from this study will help researchers determine if midodrine is safe and effective at decreasing duration of IV vasopressors and shortening ICU length of stay without increasing the risk of ICU readmission or increasing hospital length of stay.

### **POSSIBLE RISKS AND ANALYSIS OF RISK/BENEFIT RATIO**

The very common side effects of midodrine reported in previous studies include pilomotor-like reactions, paraesthesia, pruritus, and dysuria. The most common side effects are headache, supine hypertension, flushing, rash, nausea, dyspepsia, stomatitis, chills, and pain. Less common side effects comprise sleep disorders, insomnia, restlessness, excitability, irritability, and reflex bradycardia. Rare side effects are tachycardia, palpitations, abnormal hepatic function, raised liver enzymes.

These reactions rarely resulted in discontinuation of medication. These side effects may make the subject uncomfortable but do not pose any immediate harm. The subject will be assessed daily by study personnel and all efforts will be made to minimise discomfort from these side effects. Other risks that the subject may be exposed to

as a result of midodrine include hypertension, bradycardia, and tachyarrhythmias.

Patients enrolled in the study will have the same safeguards as non-study patients in an ICU setting. For patients who have stable blood pressure and adequate tissue perfusion, midodrine has been used off-label frequently to treat hypotension in our ICU. Therefore, the risks and benefits of the study drug are similar to the risks and benefits of the current standard for treating this indication in ICU patients.

Midodrine is a pregnancy category C medication. Pregnant subjects will be excluded from the study because the exposure risks of midodrine to a developing fetus are unknown. Women between the ages of 18–55, who have not had a surgical hysterectomy, will only be eligible for inclusion if they have a negative urine pregnancy test. Pregnancy testing will not need to be repeated if there is a documented negative urine pregnancy test that was obtained within 7 days prior to starting study drug, provided the woman was an ICU inpatient throughout that period of time.

## **SUBJECT PROTECTION**

Potential coercion of subjects will be avoided by obtaining informed consent by a physician who is involved in the study and is listed on the Research Staffing Form. Subjects or designated surrogate will have adequate time to decide to participate in the study. Fluctuation in a subject's mental competency is expected due to presence of sedatives or delirium. Therefore, if the subject's surrogate provides consent, a physician independent of the study will reassess the subject's mental competency using the MMSE once their Richmond Agitation Sedation Score returns to 0 or -1 or their Confusion Assessment Method for the ICU is negative. If the subject regains decision-making capacity, a study physician will obtain informed consent from the subject.

### Privacy

The screening of patients, discussions with family/proxy/legally authorised representatives, and the consent process will occur in private settings with curtains/doors closed so as to provide privacy and comfort.

## **DATA SECURITY**

### Data Monitoring

The following areas will be reviewed by the monitor for completeness and accuracy: study binders, screening log, and eligibility adherence, consent forms, data retrieved from each patient during the study, adverse event reports, and pharmacy-related study contributions. Monitoring procedures will take place on-site, at close-out. A monitoring report will be completed to verify that the monitoring plan was followed. This will be presented to the lead PI and placed in the regulatory binder. This will also be included in the FDA Annual Progress Report to ensure compliance with the FDA Code of Federal Regulations Title 21, section 312, subpart D. A Data Safety Monitoring Board is in place, which will review the data collected, as well as adverse event reports and minor deviations logs.

### Confidentiality and Security

General Protections: All study staff undergo ongoing training in proper research procedures, Good Clinical Practice, and the application of HIPAA privacy laws.

Data collection: Case report forms will be completed on site by study team members. Medical record numbers, names, dates or other identifiers will not be entered on REDCap. This platform will be used for storage and manipulation of all our de-identified data. For the different study centres, individual access groups will be formed and only the coordinating site will have access to all data.

Study file storage: All data obtained with subject identifiers will be kept in password-protected computer files behind the institutions' firewall. A crosswalk linking patient identifiers to study ID number will be maintained indefinitely by the principal investigator. Limited data will be retained on screened patients who do not meet entry criteria or who decline to participate. We will retain only the minimum data required to adequately summarise subject selection per CONSORT guidelines in the study publications. Paper records will be kept in locked filing cabinets within locked and secured offices to ensure confidentiality. All paper file contents will be shredded before disposal.

## **DISSEMINATION OF RESEARCH RESULTS**

Patients will be thanked for their time throughout the study. There is no plan to share the data at the conclusion of the trial. Because study results are likely to be published a few years after a given subject's participation, it is not feasible to send subjects follow-up with the published results. The study investigators are concerned that mailing the published manuscript and an additional thank-you note years after participation risks violating subject privacy, as mailing addresses are increasingly likely to change with passing time.

## STATISTICAL ANALYSIS PLAN

### Study aims

This randomised, controlled clinical trial evaluates the effect of oral midodrine versus placebo on time to liberation from intravenous vasopressors in ICU patients with refractory hypotension. The aim of this study is to assess the effects of midodrine treatment in patients otherwise ready for discharge from the ICU. The primary hypothesis is that midodrine treatment shortens the duration of receiving IV vasopressors compared to placebo.

### Study design

Prospective multi-centre randomised placebo-controlled trial.

### Study population and study sites

The study will enrol patients admitted to an intensive care or high-dependency unit (ICU/HDU) and meeting all eligibility criteria detailed in the study protocol. Study sites include Massachusetts General Hospital (Boston, MA, USA), Sir Charles Gairdner Hospital (Perth, Australia), and Beth Israel Deaconess Medical Center (Boston, MA, USA).

### Randomisation

Patients will be randomly allocated in a 1:1 ratio to receive either midodrine or placebo. Randomisation will be performed using a computer-generated randomisation list and will be stratified by study site. Randomisation lists will be created by an independent, unblinded study team member, under the supervision of an independent statistician. The randomisation list will be provided directly to the research pharmacy, which will be responsible for preparing and dispensing the study medications following an active order for study medications. This includes preparation and blinding of the placebo in accordance with the study randomisation schema.

### Study groups

1. Midodrine, 20 mg PO every 8 hours
2. Placebo (matched in appearance), PO every 8 hours

### Outcomes

- *Primary endpoint:*
  - Time until discontinuation of IV vasopressors, measured in hours from initiation of midodrine until discontinuation of IV vasopressors
- *Secondary endpoints:*
  - Time to ICU discharge readiness, defined as the number of days from study drug initiation to meeting discharge criteria
  - ICU length of stay, defined as the number of days in the ICU prior to transfer to the general floor
  - Hospital length of stay, defined as the total number of days in the hospital after first study drug administration
  - Rates of ICU readmission, defined as the number of patients readmitted back to the ICU after prior discharge to the general floor
- *Safety endpoints:*
  - Hypertension (increase in blood pressure to a systolic blood pressure (SBP) 20 percent higher than the predefined goal set by the primary team), bradycardia (decrease in heart rate 20 percent lower than the predefined goal set by the primary team), hemodynamically significant tachyarrhythmia (>20 percent decrease in systolic blood pressure).

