### Subject Selection

Inclusion criteria:

- At least 18 years of age
- Admitted to the intensive care services at MGH, SCGH, or BIDMC
- Requiring IV vasopressors at a rate of less than 100 mcg/min of phenylephrine, or 8 mcg/min of norepinephrine, or metaraminol 60mcg/min and unable to wean for more than 24 hours while still maintaining desired blood pressure goals.

Exclusion criteria:

- Clinical evidence of inadequate tissue oxygenation
- Clinical evidence of liver failure
- Hypovolemic shock or hypotension due to adrenal insufficiency (based on clinical suspicion or available routine testing)
- Pregnancy confirmed with a pregnancy test. Women between the ages of 18–55 who have not had a surgical hysterectomy will only be eligible for inclusion if they have a negative urine pregnancy test. Pregnancy testing will not need to be repeated if there is a documented negative urine pregnancy test that was obtained within 7 days prior to starting study drug, provided the woman was an ICU inpatient throughout that period of time.

- Chronic renal failure (serum creatinine >2mg/dL or 180 µmol/L)
- Severe organic heart disease (ejection fraction less than 30%)
- Acute urinary retention
- Pheochromocytoma (based on clinical suspicion)
- Thyrotoxicosis (based on clinical suspicion)
- Enrolment in another clinical trial
- Midodrine as pre-admission medication
- Any known allergies to midodrine
- Bradycardia (HR <50/min)
- No enteral route available

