### Study Procedures

Prior to randomisation, if subjects are eligible based on inclusion/exclusion criteria, informed consent will be obtained from participants. Once informed consent is obtained, the following information will be collected from the subject's medical record: demographics, past medical/surgical history, preadmission medication list, severity of illness at time of admission, blood pressure, aspartate aminotransferase, alanine aminotransferase creatinine, troponin, cortisol level.

The study drug or placebo will be selected based on the randomisation scheme and prepared by investigational pharmacists. All study personnel will be blinded, except the investigational pharmacist, to the treatment group of the subject. Subjects will be randomised to receive either 20 mg PO every 8 hours of midodrine, or placebo PO every 8 hours.

The study drug will be delivered in a double-blinded manner until:

- ICU discharge
- Rate of phenylephrine exceeds 100 mcg/min, or rate of norepinephrine exceeds 8 mcg/min, or rate of metaraminol exceeds 60mcg/min
- Subject exhibits signs and symptoms of organ failure or hypoperfusion
- Serious allergic adverse event related to midodrine
- Epinephrine requirement
- Death

If the blood pressure goal is met for more than 24 hours without IV vasopressors and the attending physician determines that the study drug is no longer required, the study drug may be discontinued at the discretion of the treating physician.

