### Outcomes

Study endpoints include the following:

- *Primary endpoint:*
  - Hours from initiation of midodrine until discontinuation of IV vasopressors
- *Secondary endpoints:*
  - ICU length of stay (LOS), hospital LOS, rates of ICU readmission
- *Safety endpoints:*
  - hypertension (increase in blood pressure to a systolic blood pressure (SBP) 20 percent higher than the predefined goal set by the primary team), bradycardia (decrease in heart rate 20 percent lower than the predefined goal set by the primary team), hemodynamically significant tachyarrhythmia (>20 percent decrease in systolic blood pressure).

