### Data Collection

Baseline descriptive data collection will occur on day of enrolment and includes age, sex, ethnicity, APACHE II score, admission diagnosis, pre-existing co-morbidities (diabetes, coronary artery disease, asthma, peripheral vascular disease, renal failure, psychiatric disease, musculoskeletal disease, and others) obtained from the subject, the subject's family, and the subject's medical chart. Baseline laboratory data will be recorded (haemoglobin, white cell count, alanine aminotransferase (ALT), international normalised ratio (INR), bilirubin, urea, creatinine, troponin, lactate). During the study daily SOFA scores, blood pressure goals, total fluid balances, transfused red blood cell units, administered corticosteroids, use of epidural analgesia, vasopressor and study drug start and end

times will be recorded. Days between admission and discharge from the ICU and hospital will be recorded. Readmissions to the ICU during the hospital stay will be identified through daily medical record review.

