#### *Analysis of primary and secondary outcomes*

A parametric t-test or Mann-Whitney U test will be used, as appropriate, to determine whether time from initiation of midodrine until discontinuation of IV vasopressors, time from ICU admission to ICU discharge readiness, and ICU and hospital LOS differ between groups.

A Chi-Square or Fisher's exact test will be used to test whether rates of ICU readmission and incidence of adverse events are different between treatment groups.

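### An infusion that ends at death or withdrawal of life-sustaining treatment counts as vasopressor liberation in the primary endpoint, and the SAP gives no other score for it

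*Combined protocol and SAP*

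**What the plan says.** The protocol (Outcomes) gives the primary endpoint as "Hours from initiation of midodrine until discontinuation of IV vasopressors", and the SAP (Outcomes) as "Time until discontinuation of IV vasopressors, measured in hours from initiation of midodrine until discontinuation of IV vasopressors". Neither attaches a condition on why the infusion ended.

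The SAP's Study aims section names the concept as "time to liberation from intravenous vasopressors in ICU patients with refractory hypotension". For the comparison, the SAP (Analysis of primary and secondary outcomes) says "A parametric t-test or Mann-Whitney U test will be used, as appropriate". No censoring, competing event or special score is mentioned. The Missing data section removes a patient from an outcome only when the value is missing.

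Death appears in the protocol (Study Procedures) in the list that follows "The study drug will be delivered in a double-blinded manner until". That list governs study drug and is not an endpoint rule. The SAP's Data Collection section lists vasopressor start and end times, but not the reason for a stop.

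**The concern.** A vasopressor infusion also ends when the patient dies or when life-sustaining treatment is withdrawn. Under the written definition the clock stops there and the hours enter the test like any others. If this happens early, one of the worst outcomes in the trial receives one of the best scores.

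The direction of the error depends on the arm. Such stops on midodrine would look like efficacy. Such stops on placebo would make that arm look faster and hide a benefit. At equal rates they mostly dilute the difference. The missing-data rule gives no protection, because a stop time exists.

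**Working it through.** **1. Tracing such a patient through the plan**

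| Step | Provision | Result |
|---|---|---|
| Analysis set | SAP, Statistical analysis: randomised and at least one dose | Included |
| Event | SAP, Outcomes: discontinuation, no reason required | Event at the stop time |
| Missing data | SAP, Missing data: exclude if the value is missing | Not triggered |
| Test | SAP, Analysis of primary and secondary outcomes: t-test or Mann-Whitney on hours | Early stop counted as a short time |
| Death | Protocol, Study Procedures: ends study drug | No effect on the score |

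The conclusion rests on this trace. The figures below only give a scale.

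**2. The plan's own power figure**

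The SAP (Sample size estimation) states more than 80% power for 6 h with 50 per group. It gives no SD in hours, so the figure cannot be reproduced. Solving for the SD at two-sided 0.05 and 80% power:

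SD = 6 / [(1.960 + 0.842) × √(2/50)] = 6 / (2.802 × 0.2) = 10.7 h.

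The missing SD is a separate matter.

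**3. Equal rates in both arms**

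Assumptions, not document figures: lognormal times; medians 17 h (the SAP's planning median) and 17 − 6 = 11 h; log-SD 0.7; 50 per arm; Mann-Whitney at two-sided 0.05. A share p in each arm stops at a uniform fraction of the patient's own recovery time.

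| p | Power, stop time as recorded | Power, worst rank |
|---|---|---|
| 0% | 85% | 85% |
| 5% | 82% | 77% |
| 10% | 80% | 66–68% across runs |

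At p = 20%, power with the stop time as recorded is 74%.

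The reason worst rank costs more can be seen from the probability that a placebo patient has the worse score. Without such stops it is Φ[ln(17/11) / (0.7 × √2)] = Φ(0.44) = 0.67. With worst ranks it is (1 − p)² × 0.67 + p(1 − p) + p²/2:

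- p = 5%: 0.605 + 0.0475 + 0.001 = 0.65
- p = 10%: 0.543 + 0.090 + 0.005 = 0.64

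**4. Unequal rates, no true effect**

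Assume recovery at 17 h in both arms, and non-recovery stops at 6 h in 15% on midodrine and 5% on placebo.

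- Midodrine mean: 0.85 × 17 + 0.15 × 6 = 15.35 h
- Placebo mean: 0.95 × 17 + 0.05 × 6 = 16.45 h
- Spurious difference: 1.1 h in favour of the arm with more deaths or withdrawals

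At the worst rank, the probability that a placebo patient has the worse score is 0.95 × 0.85 × 0.5 + 0.05 × 0.85 + 0.5 × 0.05 × 0.15 = 0.404 + 0.0425 + 0.004 = 0.45. This is below 0.5, so the comparison now goes against the arm with more failures.

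The simulation in step 3, with both medians at 17 h, gives a spurious difference of about 0.9 h for 15% against 5%. For 20% against 5% it gives about 1.4 h, and the test rejects in 11% of trials.

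**5. Unequal rates, true effect present**

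With medians 17 h and 11 h, such stops in 15% on placebo and 5% on midodrine lower power from 85% to 64% and the median difference from 6.0 h to 4.9 h.

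**The case against.** **The endpoint matches the hypothesis.** The primary hypothesis is a shorter period on IV vasopressors, and a patient whose infusion has ended is no longer receiving them. This has force for living patients. It does not make a death a favourable result in a trial that calls its target liberation.

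**A lowered blood pressure goal.** A reader might infer that a stop after the team lowers the goal is also misclassified. Entry requires patients "unable to wean for more than 24 hours while still maintaining desired blood pressure goals", and study drug may be stopped "If the blood pressure goal is met for more than 24 hours without IV vasopressors". The documents do not support that step:

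- The second rule governs study drug, not the endpoint.
- No section says that goals are lowered.
- The SAP records "During the study daily SOFA scores, blood pressure goals, total fluid balances", but gives no reason for doing so and does not list blood pressure values at the stop.
- A patient taken off below the first-dose goal and never restarted might have no event time at all.

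Requiring the original goal would be a different estimand, on which statisticians can disagree.

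**Such stops should be rare.** Patients are described as ready to leave the ICU apart from the infusion, are on limited vasopressor rates, and are excluded for inadequate tissue oxygenation, liver failure or an ejection fraction below 30%. The planning median is 17 h. This lowers the likely frequency but does not exclude such stops.

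**Blinding.** A reader might infer that the result will be biased. Teams do not know the arm, which makes unequal goal changes less likely, and nothing in the documents shows unequal rates. Blinding does not equalise deaths or withdrawals if treatment affects them.

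**The dilution is small and the remedy costs power.** Both points stand.

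**Conclusion.** The gap is real and narrow. As written, death or withdrawal of life-sustaining treatment while on vasopressors is scored as liberation, and early liberation if it happens early. No other rule in the protocol or SAP corrects this.

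The frequency is unknown and probably low. At equal rates of 5% to 10%, the illustrative loss is about 3 to 5 points of power. Unequal rates can produce a difference of around 1 h in the wrong direction, against a planned 6 h. These sizes rest on the assumed lognormal times, log-SD, rates and early timing. A death after a long period on vasopressors would give a long time, though it would still count as liberation.

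The argument for change is correct direction of scoring, not power. The documents do not support a claim that stops after a lowered goal are errors, or that bias is present.

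**What to change.** 1. In the SAP's Outcomes section, state that a stop due to death or withdrawal of life-sustaining treatment is not a liberation event.
2. In Analysis of primary and secondary outcomes, state that these patients stay in the analysis and are scored as not liberated, for example tied at the worst rank in the Mann-Whitney test. A score must be named, because the SAP has no rule for patients who are not liberated; without one, they could become missing and be excluded. A worst rank has no meaning in a t-test, so the rank test would need to be fixed for the primary endpoint.
3. Add one case report form field for the reason the infusion ended.
4. Report the as-recorded stop time as a sensitivity analysis.
5. Keep stops after a lowered goal in the primary analysis, with at most a sensitivity analysis using the recorded goals.

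**Cost:** a few sentences, one form field, and lower power if such stops are equally frequent in both arms (about 77% rather than 82% at 5% in the illustration). Vasopressor end times are already collected. The change concerns scoring only, not patient management.

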midodrine has been observed to effectively wean patients off continuous IV vasopressors. For patients whose only barrier to discharge from the ICU was administration of continuous medications, midodrine also appeared to decrease ICU length of stay. However, it is unknown if midodrine shortened their total hospital LOS or put the patient at risk of being readmitted back to an ICU. Additionally, midodrine appears to be well tolerated by patients when prescribed at MGH because there have been no safety reports submitted due to an adverse reaction.

No previous studies have examined the use of midodrine for the treatment of hypotension in an ICU setting. We are investigating a new indication for midodrine as the treatment for hypotension in critically ill patients. We expect that midodrine will decrease the time of patients being administered continuous vasopressors by 6 hours and therefore accelerate their readiness for ICU discharge. This has potential to have a significant impact on healthcare costs by reducing ICU and hospital LOS.

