### **Sample size estimation**

The sample size estimation is informed by the previous observational study by Levine et al. In this study, the rates of vasopressor administration decreased by 38% from  $-0.62 \pm 1.40$  mcg/min per hour to  $-2.20 \pm 2.45$  mcg/min per hour after addition of midodrine. Based on a median time of 17 h from midodrine initiation to discontinuation of IV vasopressors, the 38% reduction translates to an estimated 6 h difference. 6 h is also thought to be a meaningful time frame in terms of reduction in duration of vasopressor treatment. Accordingly, we expect that a sample size of 50 subjects per group will provide us with >80% probability (power) to detect a difference of 6 h in the primary outcome. Allowing for drop-out, our target sample size is 120.

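### Time to ICU discharge readiness is counted in days and no listed data item records when readiness is reached; whole-day scoring would probably follow and would cost this exploratory endpoint some power

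*Combined protocol and SAP*

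**What the plan says.** The SAP (Outcomes) defines the secondary endpoint as "Time to ICU discharge readiness, defined as the number of days from study drug initiation to meeting discharge criteria". It does not say whether days are whole, calendar or fractional. The primary endpoint in the same list is "measured in hours from initiation of midodrine until discontinuation of IV vasopressors".

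The SAP (Data Collection) records "vasopressor and study drug start and end" times, and "Days between admission and discharge from the ICU and hospital will be recorded". It lists no assessment of discharge criteria and no date or time at which they are met. The criteria are not set out in the protocol or the SAP.

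The SAP (Analysis of primary and secondary outcomes) tests "time from ICU admission to ICU discharge readiness", by t-test or Mann-Whitney U test. That origin differs from the one in the definition.

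On the size of effect, the protocol (Significance and Background) expects midodrine to "decrease the time of patients being administered continuous vasopressors by 6 hours and therefore accelerate their readiness for ICU discharge". The SAP (Sample size estimation) plans 50 per group, 120 in total with drop-out, "to detect a difference of 6 h in the primary outcome". No effect size is given for readiness. Secondary outcomes are exploratory (SAP, Statistical Analytical Issues).

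**The concern.** Readiness is the step by which the protocol links shorter vasopressor time to a shorter ICU stay, and unlike actual discharge it need not wait for a bed. The SAP's aim is to "assess the effects of midodrine treatment in patients otherwise ready for discharge from the ICU", so in many of these patients readiness should follow closely once the infusion stops. A shift of about 6 h is then a natural expectation, and one whole day is four times that (24/6 = 4).

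For a patient first dosed at 10:00, readiness at 15:00 or at 21:00 on the next day scores one calendar day either way, although the two differ by 6 h. At stake are power, through heavy ties in the Mann-Whitney test, and a readable estimate: the SAP allows summary by medians, and two arms 6 h apart could both show the same median day. A readiness time not recorded during the trial may also be hard to recover later in the same way at three hospitals.

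**Working it through.** **1. Can the endpoint be derived from the listed data?** It needs an origin and an end. The origin (first study drug dose) is recorded. The end (criteria first met) is not listed. Vasopressor end time is recorded, but could stand in for readiness only if being off vasopressors were the whole criterion, and the endpoint would then nearly repeat the primary. Fractional days therefore have no listed source, and whole days are the likely result.

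**2. The plan's own figure.** Power above 80% with 50 per group for 6 h belongs to the primary outcome. No SD of a time is given, so it cannot be reproduced. The largest SD consistent with 80% is

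SD = 6 / [(1.960 + 0.842) × √(2/50)] = 10.7 h.

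**3. Approximate cost of whole days.** Assume a 6 h effect on readiness and 50 per arm. Rounding to whole days adds variance 24²/12 = 48 h²; counting calendar dates adds 24²/6 = 96 h². Power = Φ(6 / [SD × √(2/50)] − 1.960).

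| SD of readiness (assumed) | Hours | Whole-day rounding | Calendar dates |
|---|---|---|---|
| 10.7 h | 80% | 65% | 54% |
| 17 h | 42% | 37% | 33% |
| 24 h | 24% | 22% | 21% |
| 48 h | 9% | 9% | 9% |

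For example, at SD 10.7 h with rounding, √(10.7² + 48) = 12.75 h and 6/(12.75 × 0.2) − 1.960 = 0.39, giving 65%.

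**4. Simulation with the planned rank test.** Inputs: 60 per arm (120 at 1:1), two-sided 0.05 and Mann-Whitney, from the SAP. Assumed: lognormal times, the same log-SD in both arms, midodrine median 6 h below placebo, first dose uniform from 08:00 to 18:00. The 17 h setting borrows the SAP's median for vasopressor discontinuation after midodrine, which is neither a readiness time nor a placebo figure. With start the clock hour of first dose, the scores are calendar days = floor[(start + time)/24], one 08:00 round = ceil[(start + time − 8)/24], and days to one decimal. Entries are ranges over repeated runs.

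| Placebo median, log-SD | Hours | Calendar days | One daily round | Days to one decimal |
|---|---|---|---|---|
| 17 h, 0.7 | 90–92% | 78–79% | 73–77% | 90% |
| 24 h, 0.5 | 86–87% | 68–72% | 73–74% | 86% |
| 24 h, 0.7 | 58–60% | 49–52% | 48–50% | 58–59% |
| 36 h, 0.7 | 28% | 25% | 26% | 28% |
| 36 h, 0.5 | 50% | 41% | 42% | 50% |

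Within a run, the loss at 17 to 24 h is between about 8 points (60% to 52%) and 18 points (86% to 68%). At 36 h it is 3 points with log-SD 0.7 and 9 with log-SD 0.5. At 48 h it was about 2 points or less with either spread.

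**5. What happens to the estimate.** In both 24 h settings the two calendar-day medians were identical in essentially every simulated trial. The mean difference survived: at 24 h, log-SD 0.7, it was 7.8 h in hours, 7.9 h in calendar days and 8.0 h with a daily round. (A 6 h gap in lognormal medians gives a mean gap of 6 × exp(0.7²/2) = 7.7 h.)

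**The case against.** The strongest reply is that a unit is not a resolution. The SAP gives both lengths of stay as day counts too, without a rounding rule, and days computed from timestamps carry the same information as hours; the one-decimal column shows this. All of the power loss comes from an assumed rounding rule. That stands as a limit on the claim. It does not dispose of it, because no readiness timestamp is listed from which to compute fractional days. The case report form is not among the documents and may hold such a field; if so, the SAP should name it.

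Second, a reader might infer that the plan states a 6 h effect on readiness. It does not. The 6 h belongs to the primary outcome, and the protocol says only that readiness is accelerated.

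Third, the larger losses need short, fairly tight times. If readiness requires more than stopping vasopressors, its median is longer; at longer medians or wider spreads, variation between patients limits power far more than the unit does. This also stands.

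Fourth, the endpoint is exploratory and carries no power claim, so no stated figure is wrong and the primary analysis, in hours from recorded times, is untouched.

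**Conclusion.** The point holds as a cheap improvement to a secondary endpoint. What rests on the text alone is that readiness is a day count, its criteria are undefined, no listed item records when they are met, and its time origin differs between the definition and the analysis section.

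The power cost is conditional on three assumptions: a shift of about 6 h in readiness, whole-day scoring, and the lognormal model. Under these it is about 8 to 18 points at medians of 17 to 24 h. At 36 h or more it is about 4 points or less with log-SD 0.7, with the tighter spread at 36 h costing about 9. It is negligible with fractional days from timestamps.

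A reader might conclude that the endpoint is too coarse to show the effect. The documents and the figures do not support that: power falls and medians can coincide, but the mean difference remains and the test still detects it in many trials.

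**What to change.** - **SAP, Outcomes:** define the endpoint in hours (or fractional days from timestamps) from first study drug dose to the first time the discharge criteria are met, with one written definition for all three sites. The content of the criteria is for the investigators to settle.
- **SAP, Data Collection:** add the date and clock time at which the criteria are first met.
- **SAP, Analysis of primary and secondary outcomes:** replace the ICU-admission origin with first study drug dose, so that definition and analysis agree.

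Cost: one case report form field, a few minutes of chart abstraction per patient, SAP wording, and agreement between sites on one definition. The daily assessment mentioned in the protocol's risk section concerns side effects, so it should not be assumed to cover this without saying so.
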